5.1.1.2 Gastrointestinal Toxicities (Nausea, Vomiting, Diarrhea)

During repeat-dose testing of GDC-9545 with monkeys, vomiting, diarrhea, and soft stools were reported. Please refer to the GDC-9545 Investigator's Brochure for further information.

GI toxicities have been reported in association with some oral SERD molecules currently in early development (see GDC-9545 Investigator's Brochure for further information). The mechanism of action of SERD associated GI toxicities is not clear and without randomized data, it is impossible to be sure if there is a true treatment effect. However, patients should be closely monitored for GI effects and any consequent sequelae such as changes in blood chemistry parameters or dehydration.

Guidelines for management of patients who develop GI toxicities are provided in [Table 1](#).

5.1.1.3 Thromboembolic Events

No evidence of thrombosis, bleeding events, or wound closure issues were seen in nonclinical studies in rats and monkeys given GDC-9545.

Thromboembolic events may occur in patients with malignancies. Against this background of malignancy, they are reported to occur commonly in patients receiving fulvestrant ($\geq 1/100$ to $< 1/10$) (eMC 2016a). There are no randomized placebo controlled data from oral SERD programs at present.

The SERM tamoxifen is reported to carry a 2- to 3-fold increased risk of thromboembolic events in the adjuvant setting (eMC 2016b).

To date, no patients treated with GDC-9545 in ongoing Phase I Study GO39932 have experienced any thromboembolic events or issues with wound healing. However, given limited data, high-risk patients (e.g., patients with a history of bleeding diathesis, coagulopathy, low platelet counts, or need for long-term anticoagulant therapy) are excluded from this study to minimize unexpected risk to patients (see Section 4.1.2).

Guidelines for management of patients who develop thromboembolic toxicities are provided in [Table 1](#).

5.1.1.4 Renal Dysfunction

Dose-dependent effects on the kidneys were observed in repeat-dose studies in both rats and monkeys given GDC-9545. Microscopic findings consistent with renal injury were observed along with mild increases in creatinine, urea, and phosphorus. Some findings were reversible during the recovery phase in monkeys at the recovery dose assessed, but no reversibility was observed in rats. Please refer to the GDC-9545 Investigator's Brochure for further information.

Renal failure or acute kidney injury are not listed as unwanted effects of fulvestrant (eMC 2016a).

Renal function tests will be closely monitored in GDC-9545 studies with serum creatinine and BUN measurements.

Guidelines for management of patients with renal dysfunction are provided in [Table 1](#).

5.1.1.5 Changes in Female Reproductive Organs and Menopausal Symptoms

GDC-9545-related effects in reproductive tissues consistent with expected pharmacology of GDC-9545 on ER degradation were observed at all doses in rats and monkeys in repeat-dose toxicity studies. Changes observed included ovarian follicular cysts (including intracystic hemorrhage), decreased uterine weight, cervical and vaginal epithelial atrophy, and decreased pituitary gland weight. Changes were partially reversible in monkeys and not reversible in rats during the follow-up period possibly due to the presence of pharmacologically active exposures of GDC-9545 at the end of the 28-day recovery period. Please refer to the GDC-9545 Investigator's Brochure for further information.

Based on the anti-estrogenic pharmacological activity of GDC-9545, its effects are anticipated to be similar to, but potentially more severe than, those of normal menopause, such as loss of muscle and bone, hot flashes, vaginal dryness or discharge, irritation, mood swings, and decreased libido.

Hot flushes and vaginal discharge have been reported in association with oral SERD molecules currently in early development. Please refer to the GDC-9545 Investigator's Brochure for further information.

GDC-9545—Genentech, Inc.
47/Protocol GO40987, Version 4

Unlike GDC-9545, the SERM tamoxifen promotes the growth of endometrial tissue in vitro, acting as an agonist of ER in that tissue (Hu et al. 2015). Endometrial changes including polyps ($\geq 1\%$ and $< 10\%$) and endometrial cancer (uncommon, $\geq 0.1\%$ and $< 1\%$) are listed as undesirable effects of tamoxifen. GDC-9545 and fulvestrant (both SERDs) are not agonistic in endometrial cells. The effects of GDC-9545 in human endometrial tissue are unknown, but endometrial agonism is not anticipated.

Changes in reproductive organs and menopausal symptoms should be managed according to local standards of care.

It is recommended that a specialist gynecological opinion be sought in the event of any abnormal bleeding from the reproductive tract.

5.1.1.6 Female Infertility

GDC-9545 has not been tested in male animals. Perturbation and arrest of the estrus cycle was observed microscopically in both female rats and monkeys. This was not reversible during the follow-up period.

It is unknown whether a longer recovery period in animals would reveal whether the observed perturbation in the estrus cycle is reversible. While this finding remains incompletely explained pending further study with a longer recovery period, any patients with concerns for future fertility should be made aware of this potential issue prior to coming onto this study. Their concerns, including fertility preservation, should be discussed prior to enrolling into any study with GDC-9545. Please refer to the GDC-9545 Investigator's Brochure for further information.

5.1.1.7 Bradycardia

During the nonclinical 4-week toxicity study in cynomolgus monkeys, GDC-9545 related reductions in heart rate or increases in RR interval were observed (surface and telemetry leads) on Day 13 at 20, 60, and 200 mg/kg and on Day 23 at 60 mg/kg. These changes were considered related to GDC-9545 but were within the normal range for cynomolgus monkey and not considered adverse.

At the time of the completion of the dose escalation portion of Study GO39932, three patients (10%) in the 90 mg cohort, had reported Grade 1 asymptomatic bradycardia. Upon further review of clinical safety data (vital signs/ECGs) patients at all dose levels were noted to have decreased heart rate from baseline and/or Grade 1 bradycardia. In all patients, bradycardia/decreased heart rate was not accompanied with clinically significant ECG changes or exercise intolerance.

Until there is a clear understanding of the clinical profile of bradycardia with GDC-9545, ECGs will continue to be collected during the study. Caution should be taken with the coadministration of drugs known to cause decreases in heart rate.

Guidelines for management of patients who develop bradycardia are provided in [Table 1](#).

GDC-9545—Genentech, Inc.
48/Protocol GO40987, Version 4

5.1.1.8 Drug–Drug Interactions

Please refer to the Section [4.4.2.1](#) for the potential DDI risks and the recommendations of the concomitant medications and foods.

5.1.2 Management of Patients Who Experience Adverse Events

If, in the investigator's or surgeon's opinion, an adverse event has the potential to delay surgery, GDC-9545 treatment should be discontinued and the patient withdrawn from the study (see Section [4.6.1](#)). Patients who discontinue study treatment prematurely will be replaced.

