3. STUDY DESIGN

3.1 DESCRIPTION OF THE STUDY

This is a Phase I, open-label, multicenter, preoperative study to assess changes in Ki67 levels and to evaluate the pharmacodynamics, pharmacokinetics, safety, and biologic activity of GDC-9545 in postmenopausal patients with Stage I–III operable ER-positive (HER2-negative) untreated breast cancer. Approximately 75 patients are expected to be enrolled in this study, at approximately 20–30 investigative sites globally.

The study consists of a screening period of up to 28 days; a treatment period of approximately 14 days, including a day for surgery; and a minimum follow-up period of 28 days. Patients will be assigned to one of three treatment cohorts (10, 30, and 100 mg; see [Figure 1](#)). GDC-9545 will be administered once daily up to and including the day of surgery (if allowed per local process) on Day 15 (± 2 days).

All patients will be required to provide a pretreatment tumor tissue sample. Archival tumor tissue from prior diagnostic formalin-fixed, paraffin-embedded cores (FFPE) may be used; however, if archival tissue is not available or is determined to be unsuitable for required testing, the patient will undergo a tumor biopsy. For the purpose of enrollment, ER, PR, and HER2 will be locally determined prior to beginning of study treatment. Patients who are not evaluable for the primary activity analysis as defined in [Section 6](#) will be replaced.

Surgery will take place on Day 15 (± 2). If surgery must be delayed >2 days, the Medical Monitor should be consulted. Surgery should be performed within 24 hours after the last dose of GDC-9545, if possible, to best observe PD knockdown with GDC-9545 in the surgical specimen. In lieu of surgical specimen, a biopsy on Day 14 may be obtained. The surgical specimen is not required if biopsy is obtained on Day 14.

All patients will be closely monitored for adverse events throughout the study and for at least 28 days after the final dose of study treatment (see [Section 5.3.1](#)). Adverse events will be graded according to the National Cancer Institute Common Terminology Criteria for Adverse Events, Version 5.0 (NCI CTCAE v5.0). In addition to the safety assessments conducted at scheduled clinic visits, patients will be contacted for a general assessment of adverse events at 24 hours post-surgery by telephone, if applicable.

[figure not shown]

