4.6 TREATMENT, PATIENT, STUDY, AND SITE DISCONTINUATION

4.6.1 Study Treatment Discontinuation

Patients must permanently discontinue study treatment if they experience any of the following:

- Any medical condition that the investigator or Sponsor determines may jeopardize the patient's safety if he or she continues to receive study treatment
- Investigator or Sponsor determination that treatment discontinuation is in the best interest of the patient
- Adverse event that, in the investigator's or surgeon's opinion, has the potential to delay surgery
- Any other adverse event that cannot be adequately managed
- Protocol violation requiring discontinuation of study treatment
- Patient is not compliant with study procedures
- Patient is lost to follow-up

The primary reason for study treatment discontinuation should be documented on the appropriate eCRF. Patients who discontinue study treatment prematurely will be replaced.

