4.6.2 Patient Discontinuation from the Study

Patients have the right to voluntarily withdraw from the study at any time for any reason. In addition, the investigator has the right to withdraw a patient from the study at any time.

Reasons for patient discontinuation from the study may include, but are not limited to, the following:

- Patient withdrawal of consent
- Study termination or site closure
- Patient non-compliance, defined as failure to comply with protocol requirements as determined by the investigator or Sponsor
- Adverse event
- Loss to follow-up

Every effort should be made to obtain a reason for patient discontinuation from the study but have not withdrawn consent. The primary reason for discontinuation from the study should be documented on the appropriate eCRF. If a patient requests to be withdrawn from the study, this request must be documented in the source documents and signed by the investigator. Patients who withdraw from the study will be replaced.

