Bradycardia	
 • Monitor patients closely for symptomatic bradycardia that may have effects on their well-being. • Patients experiencing symptomatic bradycardia should be treated and managed per standard of care. • For Grade 2 bradycardia, withhold GDC-9545 and consult with the Medical Monitor. GDC-9545 is not to be resumed without permission from the Medical Monitor. • For Grade ≥ 3 bradycardia, discontinue GDC-9545 and consult with the Medical Monitor.
Grade ≥ 3 adverse events potentially attributed to GDC-9545	
 • Discontinue GDC-9545 and consult with the Medical Monitor.

DVT = deep vein thrombosis; GFR = glomerular filtration rate; GI = gastrointestinal; IVC = inferior vena cava; PE = pulmonary embolism; ULN = upper limit of normal; VTE = venous thromboembolic events.

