5.3.1 Adverse Event Reporting Period

Investigators will seek information on adverse events at each patient contact. All adverse events, whether reported by the patient or noted by study personnel, will be recorded in the patient's medical record and on the Adverse Event eCRF.

After informed consent has been obtained but prior to initiation of study drug, only serious adverse events caused by a protocol-mandated intervention (e.g., invasive procedures such as biopsies, discontinuation of medications) should be reported (see Section 5.4.2 for instructions for reporting serious adverse events).

After initiation of study drug, all adverse events will be reported until 28 days after the final dose of study drug.

Instructions for reporting adverse events that occur after the adverse event reporting period are provided in Section 5.6.

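### Section 5.1.2 withdraws from the study a patient whose adverse event may delay surgery, although the section it cites only stops treatment, and no safety contact is specified after withdrawal

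*Combined protocol and SAP*

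**What the plan says.** Section 5.1.2 covers an adverse event that, in the view of the investigator or surgeon, could delay surgery. In that case "GDC-9545 treatment should be discontinued and the patient withdrawn from the study", with a cross-reference to Section 4.6.1.

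Section 4.6.1 concerns treatment only. Its list opens with "Patients must permanently discontinue study treatment if they experience any of the following" and includes an adverse event that "has the potential to delay surgery". The stated consequences are that the reason is documented and that "Patients who discontinue study treatment prematurely will be replaced". Study exit is not mentioned.

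Exit from the study is the subject of Section 4.6.2, which Section 5.1.2 does not cite. It gives the investigator a discretionary right to withdraw a patient and lists an adverse event under "Reasons for patient discontinuation from the study may include, but are not limited to, the following".

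Two rules on safety follow-up apply to everyone who was dosed. Section 3.1: "All patients will be closely monitored for adverse events throughout the study and for at least 28 days after the final dose of study treatment". Section 5.3.1: "After initiation of study drug, all adverse events will be reported until 28 days after the final dose of study drug". Section 5.4.2.2 sets the same limit for serious events and events of special interest.

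**The concern.** A trial can stop a drug without losing sight of the patient, and Section 4.6.1 is written that way. Section 5.1.2 goes a step further for one group, women whose adverse event is serious enough to threaten the timing of surgery. These are patients whose later safety course a sponsor would want on record.

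Safety and tolerability are a stated objective (Section 2.1). These patients stay in the safety population, because Section 6.4 counts everyone who received a dose. If a later event goes unrecorded, the patient remains in the denominator and the event is absent from the numerator. Section 5.1.1.3 describes the data on thromboembolism and wound healing as limited, and the scheduled wound assessment takes place only at the post-surgery visit, one of the contacts that study exit puts in doubt.

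**Working it through.** The plan has no statistical figure to reproduce here. The check sets the provisions side by side, then uses day counts.

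**1. What each section does when an adverse event may delay surgery**

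- Section 5.1.2: stop the drug, withdraw from the study, replace.
- Section 4.6.1 (the section cited): stop the drug, document the reason, replace.
- Section 4.6.2 (not cited): an adverse event is a possible reason for study exit, at discretion; withdrawn patients are replaced.

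Replacement follows from stopping treatment early, so study exit is not needed to obtain a replacement. By comparison, Table 1 handles a Grade 3 or higher bradycardia with "discontinue GDC-9545 and consult with the Medical Monitor", and gives the same action for other attributable Grade 3 or higher events, without study exit. That is a different trigger. It shows how the protocol usually separates drug from study, but it is not itself a contradiction.

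**2. What survives withdrawal**

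- Monitoring and reporting to 28 days (Sections 3.1, 5.3.1, 5.4.2.2), because the period runs from the last dose and not from study status.
- Follow-up of the triggering event (Section 5.5.1), which ends at resolution, stability, loss to follow-up or withdrawal of consent. Withdrawal by the investigator is not on that list.
- Membership of the safety population (Section 6.4).

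**3. What has no specified vehicle after withdrawal**

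- Section 5.3.1 has investigators ask about events whenever they are in contact with the patient. Contacts made for the triggering event also serve this purpose, but only while they last.
- Section 4.6.2 sets no contact for a withdrawn patient, and Appendix 1 has no early-termination visit.
- Section 6.4 accumulates safety data to the end of the patient's follow-up, which a site could read as ending at withdrawal.

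**4. Length of the gap**

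Let L be the day of the last dose and R the day on which the triggering event resolves or is judged stable. The 28-day point is L + 28:

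- L = 1: Day 29
- L = 8: Day 36
- L = 14: Day 42

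For a patient withdrawn when she stops, with R on or after L, the stretch with neither a scheduled contact nor follow-up of the triggering event is max(0, L + 28 − R). With L = 8 as an illustration:

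- R = 8: 36 − 8 = 28 days
- R = 15: 36 − 15 = 21 days
- R = 36 or later: 0 days

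The gap therefore runs from 0 to 28 days, depending on how long the triggering event is followed.

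**5. Contacts and checks at risk (Appendix 1)**

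- Stop before Day 8: Day 8, surgery visit, 24-hour call and Day 43, so at most 4 adverse event contacts.
- Stop after Day 8: at most 3.
- The surgery visit and the call may move or not take place on schedule. Without them the counts are 4 − 2 = 2 and 3 − 2 = 1.
- The Day 43 visit has 7 items: limited examination with wound check, vital signs, ECOG status, coagulation, ctDNA sample, adverse events and concomitant medication. Without the ctDNA sample, 7 − 1 = 6.

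**6. Number of patients**

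The documents give no rate for this trigger. Assuming 1% to 5% of 75: 0.01 × 75 = 0.75 and 0.05 × 75 = 3.75, or about 1 to 4 patients. One patient is 1/15 = 6.7% of a 15-patient cohort and 1/45 = 2.2% of the 45-patient 30 mg cohort.

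**The case against.** The strongest case on the other side has four parts.

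- **Existing text fills most of the gap.** Every patient who meets the trigger has an open adverse event, so Section 5.5.1 keeps her in contact, and those contacts also bring out new events. This stands. It reduces the gap to the time between resolution or stabilisation and the 28-day point, plus the post-surgery checks.
- **The sections can be reconciled.** Section 4.6.2 allows withdrawal for an adverse event, and Section 5.1.2 could be read as applying that power to one case. A site can follow both. Even so, a discretionary power has become a direction, supported by a reference to a section that does not contain it.
- **Withdrawal serves a purpose.** Section 4.4.3 bars other anti-cancer treatment for as long as a patient is in the study. A woman with untreated cancer whose surgery may slip could need such treatment, and withdrawal frees her to have it. This stands, and deleting the withdrawal clause without dealing with Section 4.4.3 would be a mistake.
- **Few patients are affected.** Section 1.2.2 reports no dose-limiting toxicities, related serious adverse events or events of special interest in the Phase I study at its data cutoff. This also stands, although it does not measure how often an event might delay surgery.

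A reader might go further and infer that Section 5.1.2 tells sites to stop collecting adverse events, or that these patients drop out of the safety analysis. The documents do not support either inference: the 28-day duties are tied to the last dose, and one dose is enough to enter the safety population. Nor does the clause affect the Ki67 analysis, because patients who stop early are outside the activity population and are replaced whether or not they leave the study.

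**Conclusion.** The point holds in a narrow form. Section 5.1.2 directs study exit where the section it cites only stops treatment, and no scheduled safety contact is specified after that exit. New events that arise once the triggering event has settled, and the post-surgery checks, could be missed. The duty to report remains, but it would rest on the site's initiative or the patient's own report.

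The number affected is unknown and probably small. The figure of 1 to 4 patients rests entirely on the assumed 1% to 5%. The loss of contacts rests on reading study withdrawal as ending the Appendix 1 visits; Section 4.6.2 does not say so, but it provides nothing in their place.

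The Day 43 visit can also fall before the 28-day point, because of its one-week window or because footnote k brings it forward when other therapy starts. That timing gap also affects patients who complete treatment. It is a separate point and should not be used to size this one.

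**What to change.** In Section 5.1.2, replace the study-withdrawal clause with wording to this effect: *the patient permanently stops GDC-9545, is replaced for the activity analysis, and remains in safety follow-up, with an adverse event contact by visit or telephone at 28 days or later after her last dose and the post-surgery visit where feasible, unless she withdraws consent.*

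In the same change, state that the Section 4.4.3 restriction on other anti-cancer therapy no longer applies once GDC-9545 is permanently stopped, so that follow-up cannot hold up other treatment. Any such therapy within four weeks of the last dose is already recorded under Section 4.4.

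This is a cheap improvement: a short wording change in Section 5.1.2 and one clarifying sentence on Section 4.4.3. The downside is a few extra follow-up contacts for patients who stop early.

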5.1.2.1 Dose Modifications

There will be no dose reductions allowed for GDC-9545. GDC-9545 may be held or discontinued per Section [5.1.2.3](#).

5.1.2.2 Treatment Interruption

GDC-9545 treatment may be temporarily suspended as appropriate for managing of toxicity considered to be related to study drug. The investigator and the Medical Monitor will determine the acceptable length of treatment interruption.

If a patient misses more than one dose, the Medical Monitor should be consulted about possible replacement of the patient.

5.1.2.3 Management Guidelines

Guidelines for management of specific adverse events are outlined in [Table 1](#). Additional guidelines are provided in the subsections below.

Table 1 Guidelines for Management of Patients Who Experience Specific Adverse Events

Event	Action to Be Taken
Elevation of hepatic transaminases	
 • Patients presenting with jaundice, coagulopathy, abdominal pain, or other symptoms suggestive of hepatic pathology should have their liver function tests checked and imaging of the liver performed. If the liver enzymes are elevated with no obvious malignant cause found, a hepatologist should be consulted. • Patients experiencing hepatic enzyme elevation should be treated and managed per standard of care. • Discontinue GDC-9545 for Grade ≥ 3 events and consult with the Medical Monitor.
Gastrointestinal toxicities (nausea, vomiting, diarrhea)	
 • Monitor patients closely for GI symptoms and the effects on their well-being. Patients experiencing nausea, vomiting, and diarrhea should be managed according to local standards of care, including use of anti-diarrheal agents and appropriate supportive care including hydration and dietary modification as appropriate. Infectious or alternate etiology should be excluded. • Discontinue GDC-9545 for Grade ≥ 3 events and consult with the Medical Monitor.
Venous thromboembolic events including pulmonary embolism	
 • Patients should be advised to seek immediate medical attention if they become aware of any symptoms of pulmonary embolism or DVT, such as acute onset of chest pain, shortness of breath, or swelling in extremities. • Manage and treat patients according to local standards of care (e.g., consider anti-coagulation and/or IVC filter). • Discontinue GDC-9545 for related VTE or pulmonary embolism and consult with the Medical Monitor.

Table 1 Guidelines for Management of Patients Who Experience Specific Adverse Events (cont.)

Event	Action to Be Taken
Renal toxicity (decrease in post-treatment GFR of >25% potentially attributed to GDC-9545)	
 • Patients experiencing deterioration in renal function should be treated and managed according to local standard of care. • Discontinue GDC-9545 and consult with the Medical Monitor.
Bradycardia	
 • Monitor patients closely for symptomatic bradycardia that may have effects on their well-being. • Patients experiencing symptomatic bradycardia should be treated and managed per standard of care. • For Grade 2 bradycardia, withhold GDC-9545 and consult with the Medical Monitor. GDC-9545 is not to be resumed without permission from the Medical Monitor. • For Grade ≥ 3 bradycardia, discontinue GDC-9545 and consult with the Medical Monitor.
Grade ≥ 3 adverse events potentially attributed to GDC-9545	
 • Discontinue GDC-9545 and consult with the Medical Monitor.

DVT = deep vein thrombosis; GFR = glomerular filtration rate; GI = gastrointestinal; IVC = inferior vena cava; PE = pulmonary embolism; ULN = upper limit of normal; VTE = venous thromboembolic events.

